2.3.1 Primary outcome analysis

The primary outcome combines the Conduct Problems and Hyperactivity sub-scales of the Strengths and Difficulties Questionnaire (SDQ) to measure externalising behaviours.

We will employ a two-level multilevel model to account for the clustered nature of our data, where students are nested within schools. This modelling approach assumes that the schools included in the study represent a random sample from the broader population of schools. Multilevel models are well-suited for analysing hierarchical data structures and appropriately handling the variability within schools (among students) and between schools in terms of

outcomes. These models can effectively capture and model the complex sources of variation at multiple levels of the hierarchy (Bosker & Snijders, 2011).

The two-level **random-intercept model** is described by:

$$Y_{ij} = \beta_1 + TISUK_j\tau + (Baseline_{ij})\beta_2 + FSM_j\beta_3 + \mu_j + \varepsilon_{ij}$$

- Y_{ij} is the outcome for pupil i in school j ;
- $TISUK_j$ is a binary variable denoting whether a school is assigned to the intervention (1) or the control (0);
- $Baseline_{ij}$ represents pupil-level pre-test covariates and demographic characteristics at baseline for pupil i in school j .
- FSM_j is a binary indicator denoting whether a school is above the median proportion of FSM6 (1) or below (0).
- μ_j are the school level residuals [$\mu_j \sim i. i. d N(0, \sigma_\mu^2)$]
- ε_{ij} are the individual level residuals [$\varepsilon_{ij} \sim i. i. d N(0, \sigma_\varepsilon^2)$]

This is a random intercept model because $\beta_{1j} = \beta_1 + \mu_j$ corresponds to the school-level intercept for school j and $\beta_{1j} \sim i. i. d N(\beta_1, \sigma_\mu^2)$. The total variance is decomposed into two portions: the between-school variance (μ_j) and the within-school variance (ε_{ij}). The target parameter of the intervention is the average effect on pupil outcomes captured by τ .

Regarding the risk of having several outcomes, we have designated a primary outcome and several secondary outcomes in this trial, with the primary hypothesis being addressed through the primary outcome measure. While adjustment for multiple testing is a commonly advocated strategy to mitigate the risk of type I error—incorrectly concluding an effect due to a sampling artefact—this approach has the trade-off of potentially increasing the likelihood of type II errors, where a true effect is overlooked. Given the structure of this trial, where a clear distinction is made between the primary and secondary outcomes, strict adjustment for multiple testing may not be necessary. However, it is crucial to discuss the implications of our findings in a nuanced manner in the final report, considering the context of multiple outcomes and the balance between type I and type II error risks. This approach aligns with the understanding that while avoiding false positives is important, it should not come at the cost of missing genuine effects, as discussed in Zhang, Quan, Ng, and Stepanavage (1997).

2.3.2 Secondary outcome analysis

The remaining secondary outcomes at the pupil and school staff levels follow the same equation as above. Secondary outcomes measured at the school level will be estimated using linear regression (ordinary least squares, OLS) with robust standard errors to account for potential heteroscedasticity. Since there is only one observation per school for school-level outcomes, clustering at the school level is not applicable, and robust standard errors are used to ensure valid statistical inferences in the presence of heteroscedasticity.

The **school-level model** is a linear regression set out by:

$$Z_j = \gamma_0 + \gamma_1 Intervention_j + \gamma_2 BaseS_j + \gamma_3 FSM_j + \mu_j$$
$$\mu_j \sim N(0, \sigma_\mu^2)$$

Where:

- Z_j is the outcome at the school level;
- γ_0 is the intercept;
- *Intervention* is a binary variable that equals 1 if school is within intervention arm and 0 otherwise;
- $BaseS_j$ represents the baseline covariate at the school level, which is centred around the grand mean of the school level;
- FSM_j is a binary variable indicating whether a school's % proportion of FSM pupils is above or below the median in the sample of schools participating in the trial;
- μ_j is the random error across all school
- σ_μ^2 is the residual/error variance between schools

2.3.3 Sub-group analysis

A priori in the protocol has been set out for the sub-group analysis. The sub-group analysis is exploratory and will be twofold. First, we will conduct a latent class analysis (LCA) on the intervention group to explore whether there are emerging sub-groups with differential effects. Second, we will conduct a multilevel model by sub-groups, considering that a model with interaction may be more demanding regarding power analysis. However, we will also consider a multilevel model with interaction between treatment and sub-group dummy variables for robustness check.

Latent class analysis

LCA refers to the model whose underlying indicators are all categorical, while for the continuous case, LCA is known as latent profile analysis (LPA) (Sinha, Calfee, & Delucchi, 2021). The LCA model will include the socio-demographic variables (sex, ethnicity, FSM) and primary and secondary outcomes. This will allow us to observe 'latent' groups emerging from the data.

In latent class analysis (LCA), the probability of an individual belonging to a particular latent class is modelled based on observed categorical indicators. The model assumes that the observed variables are conditionally independent given the latent class. This analysis is described by the below equation, assuming a Y_{ij} observed categorical variable for individual i in group j . The probability of observing a specific pattern of responses Y_{ij} given the latent class c is modelled using a multinomial logistic regression, typically represented as:

$$P(Y_{ij} = k | C_{ij} = c) = \frac{\exp(\lambda_{kj})}{\sum_{l=1}^K \exp(\lambda_{lj})}$$

Where:

- $P(Y_{ij} = k | C_{ij} = c)$ is the probability of observing response category k for individual i in group j given latent class c .
- K is the total number of response categories.
- λ_{kj} is the log-odds of individual i in group j selecting response category k when belonging to latent class c .

In the context of this analysis plan:

- The observed categorical variables Y_{ij} will include socio-demographic variables (sex, ethnicity, FSM) and primary and secondary outcomes.
- The latent class variable C_{ij} represents the unobserved class membership.
- will be estimated for each response category and latent class combination.

Multilevel model by sub-groups

The multilevel analysis by groups will explore the differential effects of the intervention by sex, FSM status and ethnicity, described by a modified level-1 equation as below, with φ as the main parameter of interest:

$$Y_{ij} = \beta_1 + TISUK_j\tau + (Group_{ij})\beta_2 + TISUK_j * Group_{ij})\phi + \mu_j + \varepsilon_{ij}$$

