Stepwise regression analysis will be performed to model the relationship between pre-randomisation factors and demographics on observed outcomes at 15 months. Interaction terms with the allocation arm will be included in the analysis, and a significance level of 0.1 will be used to determine which factors are to be included in the regression model. Pre-

randomisation factors will include pupil sex, FSM status and ethnicity. This analysis will be augmented by an additional analysis including participants in the intervention arm using the same pre-randomisation factors, process measures of intervention delivery, and staff changes in perceptions of trauma-informed care.

Table 6 sets out the statistical analysis for each outcome by level.

Table 6 Statistical analysis by outcome and level

Outcome	Level	Model	Covariates
Primary outcome Externalising behaviour Secondary outcomes Internalising behaviour Non-psychotic psychological distress Well-being Sense of connectedness Exclusions, suspensions and attendance at individual (CYP) level	CYP	Multi-level model	Pre-treatment scores of outcomes at CYP level Demographic factors (sex, FSM status) at CYP level
Secondary outcomes Attitudes related to TIC Well-being	School staff	Multi-level model	Pre-treatment scores of outcomes at staff level
Secondary outcomes Staff retention Staff sickness Exclusions & suspensions of CYP School attendance of CYP	School	Linear regression (OLS)	Pre-treatment scores of outcomes at school level

Sub-group analysis

The sub-group analysis will be twofold. First, we will conduct a latent class analysis (LCA) on the intervention group to explore whether there are emerging sub-groups with differential effects. LCA refers to the model whose underlying indicators are all categorical while for the continuous case, LCA is known as latent profile analysis (LPA) (Sinha, Calfee, & Delucchi, 2021). The LCA model will include the socio-demographic variables (sex, ethnicity, FSM) together with primary and secondary outcomes. This will allow us to observe 'latent' groups emerging from the data.

Second, we will conduct multilevel model by sub-groups considering a model with interaction may be more demanding in terms of power analysis. However, we will also consider for robustness check a multilevel model with interaction between treatment and sub-group dummy variable.

Missing data

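### The latent class analysis is confined to the intervention arm and so cannot show differential effects; the sub-group interaction equation also omits the baseline outcome, and its status is contradictory

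*SAP*

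**What the plan says.** SAP 2.3.3 labels the sub-group work exploratory and gives it two parts.

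**Latent classes.** The aim is stated as "we will conduct a latent class analysis (LCA) on the intervention group to explore whether there are emerging sub-groups with differential effects". On the indicators: "The LCA model will include the socio-demographic variables (sex, ethnicity, FSM) and primary and secondary outcomes". Protocol 4.1 has the same plan ("we will conduct a latent class analysis (LCA) on the intervention group") and the same rationale: "This will allow us to observe 'latent' groups emerging from the data". Neither document says whether the outcomes are baseline or follow-up scores. Neither plans to fit or assign classes in the control arm, or to compare arms within a class.

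**Models by sub-group.** SAP 2.3.3 prefers separate models, "considering that a model with interaction may be more demanding regarding power analysis", and adds: "we will also consider a multilevel model with interaction between treatment and sub-group dummy variables for robustness check". Yet the only equation printed under its sub-heading on models by sub-group, "described by a modified level-1 equation as below", is the interaction model, and its coefficient phi is named as the main quantity of interest. The terms are an intercept, TISUK, Group, TISUK x Group and the school and pupil residuals.

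The primary model in SAP 2.3.1 also contains a term that "represents pupil-level pre-test covariates and demographic characteristics at baseline", and the school FSM6 stratum. SAP Table 5 lists pre-treatment scores as covariates for pupil outcomes.

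**The concern.** A differential effect is a treatment-control difference that varies between kinds of pupil. Classes that exist only among treated pupils supply no such difference. If the indicators include follow-up outcomes, a better-outcome class and a worse-outcome class will usually emerge whatever the intervention does, and the contrast between them could be mistaken for variation in effect.

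The interaction model can address the question, but as printed it leaves out the covariate most likely to reduce residual variance. The text also leaves open whether it is the main sub-group analysis or a check on one. Separate p-values within sub-groups do not test whether effects differ.

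Sub-group effects are a listed research question (ERQ11), and SAP 2.2 gives robust sub-group analysis as one reason for targeting 100 schools.

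**Working it through.** **1. The plan's own figure.** The documents give no power or MDES for any sub-group analysis; the nearest figure is the main-effect MDES in SAP Table 4. Using the SAP 2.2 formula with both R² terms zero, ICC 0.03, J = 100, m = 160, P = 0.5 and M = 1.960 + 0.842 = 2.802:

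MDES = 2.802 x sqrt(0.03/(0.25 x 100) + 0.97/(0.25 x 100 x 160)) = 2.802 x sqrt(0.0012 + 0.0002425) = 0.1064, as stated.

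**2. The LCA.** The argument is logical; a simulation illustrates it. Each arm had 7,000 pupils, 30% of them in a more severe latent group, with sex, FSM and five binary outcomes as indicators. Every treated pupil received the same small effect and controls received none. A two-class LCA fitted separately by arm gave:

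| Arm | Class sizes | Outcome probability, low class | Outcome probability, high class |
|---|---|---|---|
| Intervention | 0.69 / 0.31 | 0.13–0.14 | 0.64–0.67 |
| Control | 0.68 / 0.32 | 0.15–0.16 | 0.67–0.69 |

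The treated classes are clearly separated although no effect varies, and nearly the same classes appear where there is no treatment. Separation within one arm reflects outcome level.

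**3. Cost of omitting the baseline outcome.** For a pupil-level sub-group with share q, equal across schools, school variance drops out of SE(phi):

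MDES(phi) = M x sqrt((1 − ICC)(1 − r²) / (N x P(1 − P) x q(1 − q)))

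Inputs: N = 13,393 and ICC = 0.015 (SAP Table 4, Randomisation column); P = 7,214/13,393 = 0.539 (Table 6; P(1 − P) is the same whichever arm holds the 7,214); q = 0.5 or 0.25 and pre-post correlation r = 0 to 0.7, all assumed. For q = 0.5 and r = 0: 2.802 x sqrt(0.985/(13,393 x 0.2485 x 0.25)) = 0.0964 SD. The SE ratio of printed to adjusted model is 1/sqrt(1 − r²).

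| r | SE excess as printed | MDES adjusted, q = 0.5 | MDES adjusted, q = 0.25 | Power as printed, at the effect the adjusted model detects with 80% |
|---|---|---|---|---|
| 0 | 0% | 0.0964 | 0.1113 | 80% |
| 0.3 | 5% | 0.0920 | 0.1062 | 76% |
| 0.5 | 15% | 0.0835 | 0.0964 | 68% |
| 0.7 | 40% | 0.0688 | 0.0795 | 52% |

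The r = 0 row is the printed model. These MDES values are before attrition; the ratios do not depend on N.

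**4. Cost of omitting the stratum.** An exact generalised least squares calculation for 78 schools of 172 pupils gives SE(phi) = 0.0343 with or without the stratum when the sub-group share is equal across schools. With shares of 40% and 12% in the two strata, SE(phi) is 0.0405 without the stratum, and 0.0403 or 0.0400 with it if it explains 30% or 60% of school variance. That is a change of 0.4% to 1.1%.

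**5. Missing baseline scores.** SAP Table 6 shows 6,179 + 7,214 = 13,393 observed and 2,232 + 1,983 = 4,215 missing. Taking the missing as additional to the observed, consistent with the Table 4 footnote, gives 4,215/17,608 = 24%. If these pupils supplied follow-up at the same rate as others and a complete-case model dropped them, the printed model's SE excess would be sqrt(0.761/(1 − r²)) − 1: about 1% at r = 0.5 and 22% at r = 0.7. Below r = sqrt(1 − 0.761) = 0.49, complete-case adjustment would lose precision.

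**The case against.** The strongest reply concerns the interaction model. The SAP calls its equation a modified one, and Table 5 specifies pre-treatment scores for the same pupil outcomes, so the baseline term may have been left out as shorthand. That reading is possible, but it has to be guessed: 2.3.2 says explicitly that pupil and staff outcomes follow the primary equation, and 2.3.3 has no such line.

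The omission costs precision and does not bias a randomised contrast. Even as printed, the MDES for phi is 0.096 to 0.111 SD, below the funder's 0.20 benchmark, although that benchmark is for the main effect. The analysis is labelled exploratory. These points stand and limit the seriousness. SAP 2.3.4 also plans a regression with allocation interactions, but it selects terms stepwise at 0.1 and does not settle which sub-group test is primary.

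For the LCA, the outcomes might be baseline scores. Such classes could act as moderators, but only if they were also assigned to control pupils, which is not planned.

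A reader might go further and infer four things that the documents do not support:

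- That dropping the stratum costs power for phi: it changes the SE by about 0–1%.
- That a loss of 15–40% is established: SAP 2.2 finds no reliable source for the pre-post correlation and assumes zero, so the loss could be nil.
- That adding the baseline score is free: Table 6 suggests otherwise.
- That the SAP commits to follow-up outcomes as indicators, or to reporting outcome severity as effect variation: neither timing nor reporting is stated.

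**Conclusion.** The LCA as specified cannot show differential effects, whichever time point its outcomes come from, because it has no control-arm classes. If follow-up outcomes are used, the classes describe outcome level. This conclusion needs no numerical assumption.

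The equation in 2.3.3 omits the baseline outcome as printed, and the section contradicts itself on the status of the interaction. With complete baseline data, the avoidable excess in SE(phi) runs from nil to 40% over r = 0 to 0.7; the documents give no value of r. A complete-case analysis could remove most of the gain. The primary estimate is not affected. The changes should be made, but the trial's main conclusion does not depend on them.

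**What to change.** - **LCA.** Form the classes from baseline variables only (sex, ethnicity, FSM, baseline SDQ and other baseline scores), in both arms pooled and blind to allocation. Then estimate TISUK x class in the primary multilevel model. Amend protocol 4.1 to match.
- **Sub-group equation.** Add the baseline outcome, for precision, and the FSM stratum, for consistency with the primary model.
- **Hierarchy.** Reconcile the two statements in SAP 2.3.3: make the interaction the sub-group test and derive within-group estimates from that model.
- **Missing baseline scores.** State how they are handled, for example by imputation or a missing indicator, so that pupils with follow-up are kept. SAP 2.3.8 currently covers imputation of missing outcome values only.

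The cost is SAP and protocol wording, plus the missing-baseline rule. No new data collection is needed, since baseline measurement is already planned.

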¹⁰ Average school size in England is 986, average year size is 200 and accounting for a potential 20% not consenting, hence, cluster size 160.

		Scenario 1
Number of participants	Intervention	8,000
	Control	8,000
	Total	16,000

4. Outcome measures

The impact of the intervention is measured through a primary outcome at the CYP level, the combined conduct and hyperactivity scale scores from the Strengths and Difficulties Questionnaire (SDQ) at CYP level, and a list of secondary outcomes at CYP, school staff and school level. Table 5 sets out the primary and secondary outcomes.

Table 5 Primary and secondary outcomes

Outcome	Primary / Secondary	Level	Scales of instrument	Description and source
Externalising behaviours	Primary	CYP	SDQ – combined conduct and hyperactivity scales (0-20)	The Strengths and Difficulties Questionnaire (SDQ) is a brief questionnaire designed to assess behavioural patterns in children and adolescents aged 3-16. It consists of 25 items covering various psychological attributes, including positive and negative aspects. YEF utilises the Strengths and Difficulties Questionnaire in all its projects (where appropriate) to ensure uniformity and facilitate comparisons across various evaluations. Further information about the SDQ is available here: https://www.sdqinfo.org/ .

Outcome	Primary / Secondary	Level	Scales of instrument	Description and source
				Data will be collected electronically by the evaluation team (Ipsos) using Dimensions ¹¹ .
Internalising behaviour	Secondary	CYP	SDQ – combined emotional problems and peer problems scales (0-20)	SDQ Data will be collected electronically by the evaluation team (Ipsos) using Dimensions.
Prosocial behaviour	Secondary	CYP	SDQ – Prosocial behaviour scale (0-10)	SDQ Data will be collected electronically by the evaluation team (Ipsos) using Dimensions.
Total difficulties	Secondary	CYP	SDQ – Total score (sum of internalising and externalising behaviours scales (0-40))	SDQ Data will be collected electronically by the evaluation team (Ipsos) using Dimensions.

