The primary outcome is externalising behaviour at pupil level in Year 8 measured by the Strengths and Difficulties Questionnaires (SDQ) – Combined Conduct and Hyperactivity Scale. There is a baseline measurement before the start of the intervention and then a follow-up measurement once the intervention ends, namely, 15 months after randomisation. The secondary outcomes at pupil levels in Year 8 consist of internalising behaviour, prosocial behaviours, total difficulties, non-psychotic psychological distress, well-being, sense of connectedness, exclusions and suspensions, and school attendance. Other secondary outcomes at the school staff level are attitudes related to TIC, school staff's well-being, school staff retention and sickness. Finally, the % of exclusions, suspensions and attendance of CYP at the school level will be collected. Detailed instruments for each outcome are described in Table 1 below.

Table 1 Summary of trial design

Trial design		Two-arm and cluster randomised at the school level
Unit of randomisation		School
Stratification variables (if applicable)		Binary indicator of school-level percentage of pupils eligible for Free School Meals (Below median percentage vs. At or above median percentage)
Primary outcome	variable	(CYP) Externalising behaviour
	measure (instrument, scale, source)	SDQ – Combined conduct and hyperactivity scale scores (0-20) (Survey)
Secondary outcome(s)	variable(s)	(CYP) Internalising behaviour
		(CYP) Prosocial behaviour
		(CYP) Total difficulties
		(CYP) Non-psychotic psychological distress

		
(CYP) Well-being
 
(CYP) Sense of connectedness
 
(CYP) Exclusions & suspensions
 
(CYP) School attendance
 
(School staff) Attitudes related to TIC
 
(School staff) Well-being
 
(School) Staff retention
 
(School) Staff sickness
 
(School) Exclusions & suspensions of CYP
 
(School) School attendance of CYP

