	
measure(s) (instrument, scale, source)
	
(CYP) Internalising behaviour: SDQ – Combination of emotional regulation and peer problems (0-20) (Survey)
 
(CYP) Prosocial behaviour: SDQ – sub-dimension of prosocial behaviour (0-10) (Survey)
 
(CYP) Total difficulties: SDQ – Combination of sub-dimensions of conduct, hyperactivity, emotional regulation, and peer problems (0-20) (Survey)
 
(CYP) Non-psychotic psychological distress: General Health Questionnaire (GHQ12) (0-12) (Survey)
 
(CYP) Well-being: Short Warwick Edinburgh Mental Well-being Scale (7-35) (Survey)
 
(CYP) Sense of connectedness: School Connectedness Scale (Survey)
 
(CYP) Exclusions & suspensions: administrative records
 
(CYP) School attendance: administrative records
 
(School staff) Attitudes related to TIC: Attitudes Related to Trauma Informed Care (ARTIC) (Survey)
 
(School staff) Well-being: Short Warwick Edinburgh Mental Well-being Scale (7-35) (Survey)
 
(School) staff retention: administrative records

		
(School) staff sickness: administrative records
 
(School) Percentage of exclusions & suspensions of CYP: administrative records
 
(School) Percentage of school attendance of CYP: administrative records

Baseline for primary outcome	variable	(CYP) Externalising behaviour
	measure (instrument, scale, source)	SDQ – Combined conduct and hyperactivity scale scores (Survey)
Baseline for secondary outcome	variable	
(CYP) Internalising behaviour
 
(CYP) Prosocial behaviour
 
(CYP) Total difficulties
 
(CYP) Non-psychotic psychological distress
 
(CYP) Well-being (CYP) Sense of connectedness
 
(CYP) Exclusions & suspensions
 
(CYP) School attendance
 
(School staff) Attitudes related to TIC
 
(School staff) Well-being
 
(School) Staff retention
 
(School) Staff sickness
 
(School) Percentage of exclusions & suspensions of CYP
 
(School) Percentage of school attendance of CYP

	measure (instrument, scale, source)	
(CYP) Internalising behaviour: SDQ – Combination of emotional regulation and peer problems (0-20) (Survey)
 
(CYP) Prosocial behaviour: SDQ – sub-dimension of prosocial behaviour (0-10) (Survey)
 
(CYP) Total difficulties: SDQ – Combination of sub-dimensions of conduct, hyperactivity, emotional regulation, and peer problems (0-20) (Survey)

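### The latent class analysis assumes its indicators are independent within class, yet its indicator list includes SDQ Total Difficulties and the two scores that add up to it

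*SAP*

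**What the plan says.** SAP 2.3.3 plans two kinds of sub-group work and labels both as exploratory: "The sub-group analysis is exploratory and will be twofold". The first is the latent class analysis: "First, we will conduct a latent class analysis (LCA) on the intervention group to explore whether there are emerging sub-groups with differential effects".

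On the model it says: "The model assumes that the observed variables are conditionally independent given the latent class". On the inputs it says: "The LCA model will include the socio-demographic variables (sex, ethnicity, FSM) and primary and secondary outcomes". No outcome is excluded, and no residual dependence between indicators is allowed for. Protocol 4.1 gives the same indicator list.

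Three of the outcomes on that list are linked:

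- Externalising behaviour is the primary outcome: conduct plus hyperactivity, range 0-20.
- Internalising behaviour is a secondary outcome: emotional plus peer problems, range 0-20.
- Total Difficulties is a secondary outcome in SAP Table 1 and has its own research question, ERQ4. Protocol section 4, Table 5 defines it as the "sum of internalising and externalising behaviours scales", range 0-40.

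The SAP gives no rule for choosing the number of classes, does not say how scores become categories, and plans no check of the independence assumption.

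**The concern.** If one indicator is the sum of two others, the three cannot be independent of each other inside a class in which the components vary. The model as stated has only one device for explaining association between indicators, which is class membership. It therefore tends to cut the externalising-internalising plane into pieces and call each piece a class.

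At stake is the meaning of the classes. Their number and shape could reflect the same SDQ items being counted twice rather than any grouping of pupils, and the analysis exists to look for such groupings.

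**Working it through.** The documents give no figure for this analysis (no number of classes, fit criterion or power), so there is nothing to reproduce.

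**1. The identity.** Write E for externalising, I for internalising and T for Total Difficulties. Protocol Table 5 gives T = E + I, and the ranges agree: 20 + 20 = 40. The SAP's Table 1 prints 0-20 for the total, but it names the same four sub-scales.

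**2. What it does to the assumption.** Within class c, Cov(E, T | c) = Var(E | c) + Cov(E, I | c). If E and I are independent within the class, as the model requires, this equals Var(E | c). That is zero only if E is constant in the class. The same argument makes I constant. Raw scores would then need one class for each pair of values, up to 21 × 21 = 441. Banding loosens the identity but leaves strong dependence.

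**3. Size of the dependence.** SAP Table 6 gives externalising in the intervention arm as 7.62 (SD 4.37); 7.5 (4.3) was used. For internalising, 6.5 (4.0) is assumed. With r the correlation of E and I:

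- r = 0: corr(E, T) = 4.3 / √(18.49 + 16.00) = 4.3 / 5.87 = 0.73.
- r = 0.4: Cov(E, T) = 18.49 + 6.88 = 25.37 and Var(T) = 34.49 + 13.76 = 48.25, so corr(E, T) = 25.37 / (4.3 × 6.95) = 0.85.

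**4. Simulation with one true class.** A single homogeneous population was generated with E, I, either no or four further outcomes, and three independent binary demographics. All outcomes shared the correlation r. Latent class models were fitted by EM with several starts, and the number of classes was chosen by BIC. The n of 7,214 is the intervention-arm count in SAP Table 6. SAP Table 4 prints that figure under control, so n = 1,000 was also run for the median split. There were five replicates per tertile setting and four per median-split setting.

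| Banding (largest model tried) | Other outcomes | n | r | Classes without T | Classes with T |
|---|---|---|---|---|---|
| Tertiles (6) | 0 | 7,214 | 0 | 1 | 6 |
| Tertiles (6) | 0 | 7,214 | 0.2 | 2 | 6 |
| Tertiles (6) | 0 | 7,214 | 0.4 | 2 | 6 |
| Tertiles (6) | 4 | 7,214 | 0 | 1 | 6 |
| Tertiles (6) | 4 | 7,214 | 0.2 | 2 | 6 |
| Tertiles (6) | 4 | 7,214 | 0.4 | 3 | 6 |
| Median split (5) | 4 | 1,000 | 0 | 1 | 3 |
| Median split (5) | 4 | 1,000 | 0.2 | 2 | 3 |
| Median split (5) | 4 | 1,000 | 0.4 | 2 | 4-5 |
| Median split (5) | 4 | 7,214 | 0 | 1 | 3 |
| Median split (5) | 4 | 7,214 | 0.2 | 2 | 5 |
| Median split (5) | 4 | 7,214 | 0.4 | 3 | 5 |

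Replicates agreed in every row except the one showing 4-5. For scale, at r = 0 with tertiles and no other outcomes, BIC relative to one class in one data set was -4,337 (two classes) and -8,502 (six classes) with T. Without T, in a separate data set, it was +63 and +323.

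A further one-class simulation (n = 3,000, five scores, one to six classes) chose 6 in every setting with T. Without T and with tertiles, it chose 1 class at r = 0 and 2-3 at r = 0.3.

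**5. Would continuous indicators cure it?** At n = 3,000 with five scores, one true class and T excluded, normally distributed continuous scores gave 1 class at r = 0, 3 at r = 0.3 and 4 at r = 0.5. Right-skewed integer scores on 0-20 gave 6, the maximum tried, at every r including 0. So a switch to continuous indicators can itself create extra classes.

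**The case against.** Five points can be made for the plan.

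- **No commitment to BIC.** The SAP names no rule, and analysts might cap the number of classes or weigh class size and interpretability. This stands. A reader might infer that the analysis is bound to report spurious sub-groups; the documents do not support that. Nor do the simulations estimate how many classes would be reported, since most of the results with the total lie at the largest model tried.
- **Other outcomes also correlate.** Mental-health scores from the same pupils are unlikely to be independent, and correlation alone produced 2-3 classes without the total. This stands. The clean contrast of one class against six holds only at r = 0, and dropping the total is not sufficient by itself.
- **The indicator list may be shorthand.** Read literally it takes in staff and school outcomes, so some selection must happen, and SAP Table 5 does not list Total Difficulties among the modelled outcomes. This helps only a little: SAP Table 1 and ERQ4 both make the total a secondary outcome, and nothing removes it from the latent class analysis.
- **It is exploratory.** True. A reader might infer that the plan will treat the classes as established sub-groups with their own treatment effects. The SAP specifies no effect estimate by class; differential effects are modelled separately by sex, FSM status and ethnicity. An analysis of the intervention arm alone could not show differential effects in any case, and removing the total does not change that.
- **The trial's main results are safe.** Also true, and it limits the weight of the point.

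None of these restores the stated assumption.

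**Conclusion.** The point holds in a limited form. The stated indicator list contradicts the stated independence assumption by construction. That conclusion needs only the two documents and does not depend on any simulation.

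The consequence is conditional. If the number of classes is chosen by BIC or a similar criterion, the total pushes the model towards classes that are arithmetic artefacts. With tertile bands the choice was 6 (the maximum) with the total, against 1 without it when the other outcomes are independent and 2-3 when they correlate at about 0.3. With a median split the gap is narrower: 3 against 1 at r = 0, and 4-5 against 2-3 at r = 0.4. These figures rest on assumed correlations, an assumed internalising mean and SD, assumed banding and an assumed selection rule.

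The damage is confined to the exploratory latent class analysis. The primary and secondary treatment-effect estimates are unaffected.

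**What to change.** In SAP 2.3.3, and to match in Protocol 4.1:

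- Exclude SDQ Total Difficulties from the latent class indicators, and keep externalising and internalising.
- Do not enter any other total alongside its own sub-scales. GHQ-12 is an example: Protocol Table 5 lists a total score and three sub-scales.
- Check bivariate residuals before interpreting any class, because correlation among the remaining outcomes can still generate extra classes.
- Do not make a switch to continuous indicators a condition, given the result with skewed scores.

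Stating the rule for the number of classes in the same edit would remove the main assumption above.

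The cost is a few sentences and one routine diagnostic, with no new data. No information is lost, since the total can be recovered from the two scores kept, and Total Difficulties remains a secondary outcome under ERQ4. The edit should be made before the classes are fitted.
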